6.2. Data Handling Methods

6.2.1. Missing Data

Missing Data Handling

1) Multiple Imputation (MI) Method

The MI method will be applied for the sensitivity analysis of the primary endpoint. For all subjects in the FAS, missing data of the primary endpoint—the score of Part III (Motor Examination) of the Movement Disorder Society-Unified Parkinson's Disease Rating Scale (MDS-UPDRS) at 12 weeks post-dose (evaluation time point: ≥ 12 hours after the last dose of anti-PD drug)—will be imputed. The imputation rules are detailed in Section [11.1](#) of the Appendix in SAP.

2) Last Observation Carried Forward (LOCF) Method

The LOCF method will be applied for sensitivity analysis of the primary endpoint. For all subjects in the FAS, missing data of the primary endpoint—the score of Part III (Motor Examination) of the Movement Disorder Society-Unified Parkinson's Disease Rating Scale (MDS-UPDRS) at Week 12 (assessment time point: ≥ 12 hours after the last dose of anti-PD drug)—will be imputed. Missing data will be imputed using the last non-missing observation prior to the visit after baseline (excluding baseline).

3) Missing Date:

For incomplete date data, the dates in the list will be presented according to the actual circumstances. The missing date imputation rules are as follows:

Missing AE Onset Date

- Only day missing: If the year and month of the AE onset date are the same as the year and month

of the first dose date, and the AE end date is confirmed to be no earlier than the first dose date or missing, then the first dose date will be used as the AE onset date. Otherwise, impute as the 1st day of the month.

- Month and day missing: If the year of the AE onset date is the same as the year of the first dose date, and the AE end date is confirmed to be no earlier than the first dose date or missing, then the first dose date will be used as the AE onset date. Otherwise, impute as January 1 of that year;
- Year, month, and day missing: Impute with the subject's first dose date.

Missing AE End Date

- Only day missing: impute as the date of the last day of the month;
- Month and day missing: imputed as December 31 of that year;
- Year, month, and day missing: no imputation.

The imputation of the end date should not be earlier than the onset date.

Missing Or Incomplete Start Dates Of Previous And Concomitant Medications/Non-Drug Therapies

- Only day missing: impute as the first day of the month;
- Month and day missing: impute as January 1 of that year;
- Year, month, and day missing: no imputation.

Missing Or Incomplete End Dates Of Previous And Concomitant Medications/Non-Drug Therapies

- Only day missing: Impute as the last day of that month;
- Month and day missing: impute as December 31 of that year;
- Year, month, and day missing: no imputation.

The imputation of the end date should not be earlier than the onset date.

6.2.2. Derived and Transformed Data

No derivation or transformation of other data will be performed, except for the calculation of certain study endpoints based on collected data.

Definitions and calculation methods for drug exposure and compliance are as follows:

Drug exposure will be calculated based on the eCRF page "Administration of Investigational Product":

- Actual total exposure (mg):
 - For placebo, the actual total exposure (mg) = 0 mg;
 - For the TJ0113 capsule group, the actual total exposure (mg) = actual cumulative number of doses administered (capsules) \times 100 mg.

- Total actual exposure days (days) = Sum of actual dosing days, calculated by accumulating the interval days between the start and end dates of actual dosing collected in the eCRF to determine the subject's actual dosing duration. If a dose is missed, it will be recorded as a separate line in the eCRF, with the "Actual Daily Dose" recorded as "0 capsules." When calculating the total exposure days, the corresponding number of missed days should be deducted based on the start and end dates of the missed doses.
- Actual dose level (mg/day) = Total actual exposure / Total exposure days.

Medication compliance (%) will be calculated based on the eCRF pages "Investigational Product Dispensing" and "Investigational Product Accountability":

- Total cumulative number of drug dispensed (capsules) = Sum of the number of drug dispensed.
- Total number of recovered drug (capsules) = Sum of recovered drug.
- Cumulative lost/contaminated drug count (capsules) = Sum of lost/contaminated capsules.
- Actual cumulative administered dose (capsules) = Actual cumulative total dispensed dose (capsules) - Actual cumulative total recovered dose (capsules) - Actual cumulative lost/damaged dose (capsules)
- Planned cumulative dose (capsules):
 - For the 200 mg cohort: Planned cumulative dose (capsules) = Planned dosing days (days) \times 2;
 - For the 400 mg cohort: Planned cumulative dose (capsules) = Planned dosing days (days) \times 4;

Planned dosing days (days) = Date of last drug recovery – Date of first dose dispensing. If the last drug recovery visit is the withdrawal visit and the last drug recovery date $>$ (first dose dispensing date + 84 days), replace it with (first dose dispensing date + 84 days). If the last drug recovery visit is an unscheduled visit and the date of last drug recovery is $>$ the date of study completion/withdrawal, then the date of study completion/withdrawal should be used instead. If there is no record of drug recovery after the last dose dispensing and the study has ended, the date of the next visit after the last dose dispensing or the study completion/withdrawal date, whichever is earlier, should be used. If the date of the next visit after the last dose dispensing or the study completion/withdrawal date exceeds (the first dose dispensing date + 84 days), then (the first dose dispensing date + 84 days) should be used instead.

- Medication compliance (%) = Actual Cumulative Dose Administered (tablets) / Planned Cumulative Dose (tablets) \times 100.

For subjects who were randomized but did not receive any investigational product, or who were randomized but received different dose groups, the compliance will be 0.

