### 6.3 Drug Dispensing

All investigational products will be randomized by the IWRS, and each subject will be assigned multiple drug numbers by visit during the study. The system will automatically record the drug allocation information of each subject, including the date of drug dispensing and drug number. The drug manager should dispense the drugs according to the drug number

assigned by the system at each visit.

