### **7.3 Compliance of Study Subjects**

During the study, the administration of both the investigational product and the background medication for PD will be recorded in the eCRF. Subjects' medication compliance will be calculated according to the quantity of investigational product dispensed and returned and combined with the diary card.

Calculation method for medication compliance: medication compliance = actual dose/planned dose \* 100%.

If the subject's compliance is between 80% and 120%, it means that the compliance is good; if the subject's compliance is < 80% or > 120%, it indicates poor compliance.

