3.4.3. Assessment of Skeletal Muscle Mass and Function

The exploratory skeletal muscle mass and function assessment indicators in this trial include ASMI, muscle strength (handgrip strength), and the 6-meter walk test. The specific testing indicators should be determined based on the actual operations of each center.

4. Sample Size

The sample size of this study is not determined based on the formal statistical assumptions and it is expected to include approximately 150 subjects with early-stage PD, who will be randomized in a 1:1 ratio into two cohorts (Cohort 1: 200 mg dose group; Cohort 2: 400 mg dose group). Within each cohort, the subjects will be randomized into the TJ0113 capsules group and the placebo group in a ratio of 2:1, with approximately 50 subjects receiving TJ0113 capsules and approximately 25 subjects receiving the placebo. In this study, there will be approximately 50 subjects in each of the TJ0113 capsules 200 mg group, TJ0113 capsules 400 mg group and the placebo group.

5. Analysis Sets

Full analysis set (FAS): including all randomized subjects who have received at least one dose of investigational product.

Per-protocol set (PPS): including subjects in the FAS who have not experienced major protocol deviations that affect the primary efficacy endpoint.

Safety Set (SS): Includes all subjects who received at least one dose of the investigational product and underwent at least one post-dose safety assessment.

Demographics and baseline characteristics will be analyzed based on FAS, the efficacy analyses will be performed based on both FAS and PPS, and the safety analyses will be performed based on SS.

6. Statistical Analysis Methods

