6.9. Compliance

Based on the FAS, analyze and tabulate the compliance of the subjects. For subjects who were randomized but did not receive any investigational product, or who were randomized but received different dose groups, the compliance will be 0. Summarize descriptively the continuous and categorical (<80%, 80% - 120%, >120%) outcomes for the following indicators: total cumulative number of drugs dispensed (capsules), total cumulative number of drugs recovered (capsules), total cumulative number of drugs lost/damaged (capsules), actual cumulative number of drugs administered (capsules), planned duration of drug administration (days), planned cumulative number of drugs administered (capsules), and medication compliance (%). For specific definitions and calculation methods, please refer to Section [6.2.2.](#)

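### The SAP scores a dosed patient who received another dose group as 0% compliant, contrary to the actual/planned formula in Protocol 7.3, and so can place an overdosed patient in the <80% category

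*SAP*

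**What the plan says.** - **Zero rule.** SAP 6.2.2 ends its compliance definitions with a fixed value of 0 for two kinds of patient, those who took no product and those given a dose group other than their own. The second half of the rule reads: "or who were randomized but received different dose groups, the compliance will be 0". SAP 6.9 repeats the rule for the compliance table. Neither section defines what counts as receiving a different dose group.
- **Protocol formula.** Protocol 7.3 gives "medication compliance = actual dose/planned dose \* 100"%, with 80% to 120% good and anything outside poor. It has no override to 0. SAP section 8 lists no changes to the protocol's planned analysis.
- **Table and population.** SAP 6.9 bases the table on the FAS and reports the percentage, the categories <80%, 80%–120% and >120%, and the capsules dispensed, recovered, lost and administered. SAP section 5 admits to the FAS only patients with at least one dose.
- **Exposure.** This is a separate derivation in SAP 6.2.2, taken from a different eCRF page. One line reads "For placebo, the actual total exposure (mg) = 0 mg". The line for the active group multiplies the capsules administered by 100 mg. Neither carries an override for a wrong dose group. SAP 6.12.1 tabulates total mg, days and mg/day on the SS.
- **Dispensing.** Under Protocol 6.3, "each subject will be assigned multiple drug numbers by visit during the study", and the system records each number and date.

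**The concern.** The SAP foresees that a patient may get the wrong dose and then replaces a calculable ratio with a constant. The constant is wrong in size for every dosed patient it reaches. For a patient who took too much it is also wrong in direction, because it moves the patient from the top category to the bottom one. It departs from the protocol without being declared.

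A compliance table should let a reader tell under-dosing from over-dosing, and this rule removes that distinction for the patients in whom the dose went wrong. A smaller, related question arises for exposure: the two exposure lines do not say what happens when a patient receives active capsules in place of placebo, or the reverse.

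**Working it through.** The plan states no figure to reproduce, so the check applies its own definitions.

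**Inputs**
- Treatment runs from D1 to D84 (Schedule of Activities), which is 84 dosing days. The SAP's planned days (last recovery minus first dispensing) also give 84 when V2 is D-1 and V6 is D84, as there is no Day 0.
- Planned capsules (SAP 6.2.2): 84 × 2 = 168 in the 200 mg cohort and 84 × 4 = 336 in the 400 mg cohort.
- Supply intervals from the visit schedule: 7, 21, 28 and 28 days (sum 84).
- Assumptions: visits on schedule, and every supplied dose taken.

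**Step 1. Whom the rule can reach.** Patients who took no product are outside the FAS, so that half of the clause has no effect in the FAS table. Only the different-dose-group half can act, and only on patients who took at least one dose.

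**Step 2. Wrong regimen throughout**
- Assigned 200 mg, took the 400 mg regimen: 336/168 = 200%, category >120%. SAP: 0, category <80%.
- Assigned 400 mg, took the 200 mg regimen: 168/336 = 50%, category <80%. SAP: 0, same category, wrong value.

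**Step 3. Wrong regimen for one interval of d days**, if that is enough to trigger the rule
- Assigned 200 mg: [2(84 − d) + 4d]/168
- Assigned 400 mg: [4(84 − d) + 2d]/336

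| d | 200 mg patient on 400 mg regimen | 400 mg patient on 200 mg regimen | SAP |
|---|---|---|---|
| 7 | 182/168 = 108.3% | 322/336 = 95.8% | 0 |
| 21 | 210/168 = 125.0% | 294/336 = 87.5% | 0 |
| 28 | 224/168 = 133.3% | 280/336 = 83.3% | 0 |

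Four of these six values lie in the protocol's good-compliance band, and the other two are above 120%. The rule would put all six below 80%.

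**Step 4. Effect on an arm mean.** Take 50 patients, 49 of them at 100%. With one patient at 200%, the true mean is (4,900 + 200)/50 = 102.0% and the reported mean is 4,900/50 = 98.0%. With one patient at 50%, the true mean is 99.0% against the same 98.0%.

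**Step 5. What the other columns show.** The 200 mg patient on the 400 mg regimen throughout still has 336 capsules administered, 336 × 100 = 33,600 mg, and 33,600/84 = 400 mg/day. These are correct. The patient's record would therefore show 336 capsules taken beside 0% compliance.

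**Step 6. Active/placebo swaps in the exposure derivation**, if the two lines are applied by randomized group
- Placebo-group patient given active capsules for one interval: 7 × 2 × 100 = 1,400 mg to 28 × 2 × 100 = 5,600 mg at two capsules a day, or 2,800 to 11,200 mg at four. Reported: 0 mg.
- 200 mg patient given placebo for one interval: reported 168 × 100 = 16,800 mg. Taken: 2 × (84 − 28) × 100 = 11,200 mg to 2 × (84 − 7) × 100 = 15,400 mg.

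**The case against.** The strongest reply is that the rule touches one derived percentage and little else. Exposure has its own source and no override, and the compliance table prints the capsule counts. Protocol 9.5.3 has adverse events from overdose or medication error recorded, and SAP 6.5 lists all patients with protocol deviations. The primary and secondary models (SAP 6.10.1.1 and 6.10.2) do not use compliance, and the PPS definition does not name it. All of this stands and limits the size of the point. It does not make the 0 correct.

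A reader might infer more than the documents support:

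- **That overdosed patients appear to have taken nothing.** Step 5 shows otherwise: capsules, mg and mg/day survive. A patient who takes 3 instead of 2 capsules a day from the assigned supply gets 3/2 = 150% and falls in >120%, unless that too is read as a different dose group.
- **That a single wrong supply zeroes a patient.** Dispensing by visit makes a one-interval error possible, but the SAP does not say whether one interval or the whole treatment is meant. Step 3 is conditional for that reason.
- **That placebo exposure is fixed by randomized group.** The placebo line can equally mean the product taken, and 0 mg is then right. The text is ambiguous.
- **That events on misdispensed active drug will be counted under placebo.** The SAP does not say whether the SS is summarised by randomized or received treatment, and silence does not establish the outcome.

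**Conclusion.** The zero clause is wrong as written. It conflicts with Protocol 7.3, is not declared in SAP section 8, and in the FAS table can act only on patients for whom a real ratio exists. In the clearest case it turns 200% into 0 and moves the patient from >120% to <80%; in the opposite case it turns 50% into 0. If one interval suffices, true values between 83.3% and 133.3% are also lost.

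The consequence is small. It is confined to the compliance percentage and category of patients who should be rare, at 4 points on a 50-patient arm mean for one patient at 200%. The exposure issue arises only for active/placebo swaps and only under one reading of the text. PPS membership would be affected only if compliance were used to define a major deviation, which neither document states. The figures assume on-schedule visits and full intake of what was supplied.

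**What to change.** - Delete the different-dose-group clause from SAP 6.2.2 and 6.9. Calculate compliance for these patients as actual over planned dose under Protocol 7.3, with planned dose taken from the assigned regimen.
- Identify them in a separate listing that gives the supply received and the dates.
- For active/placebo swaps only, where a capsule count misleads, compute mg from the content of the supplies actually received, using the drug numbers that Protocol 6.3 already has recorded and decoding them after unblinding. Word the placebo line so that 0 mg attaches to placebo product, not to a placebo-group patient who took active capsules. Decoding does not help with 200/400 mg errors, because both doses use the same 100 mg capsule (Protocol 6.1); the capsule count already shows those.
- As a clarification, state in SAP section 5 whether the SS is summarised by treatment received and where patients with mixed supply are placed.

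The cost is a few sentences in the SAP and one listing. No new data are needed, and no result changes if no misdispensing occurs.

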6.3. Subject Distribution Analysis

Based on all subjects who signed the informed consent form, the number and percentage of subjects in the following categories will be summarized:

- Successfully screened subjects
- Screen failures (reasons for screen failure)
- All randomized subjects (including those randomized at each center)

Based on all randomized subjects, the number and percentage of subjects in the following categories will be summarized:

- Randomized subjects who did not receive any investigational product
- Randomized subjects who received any dose of the investigational product
- Ongoing
- Completion of the study
- Early withdrawal of study (Reasons for early withdrawal of study)

List the reasons for screen failure and early withdrawal of study in detail.

6.4. Subject Analysis Set Classification

Based on all randomized subjects, calculate the number and percentage of subjects included in the FAS, PPS, and SS. Additionally, provide a detailed list of reasons for subjects excluded from each analysis set.

6.5. Protocol Deviations

Based on the FAS, categorize and summarize significant protocol deviations, and provide a detailed listing of all subjects with protocol deviations.

6.6. Demographic Data and Baseline Characteristics Analysis

Based on the FAS, summarize and tabulate the demographic data and baseline characteristics of the subjects.

Demographic data of subjects include:

- Age (years)
- Age groups (<18 years, 18-65 years, 66-75 years, >75 years)
- Gender (Male, Female)
- For females, is the subject of childbearing potential (yes, no (postmenopausal, sterilization surgery, ovarian failure, other), uncertain if menopausal)
- Ethnicity (Han, Others)
- Height (cm)
- Weight (kg)
- Body Mass Index (kg/m²)

The baseline characteristics of subjects include:

- Random stratification factors:
 - Is the subject currently on stable levodopa-based anti-PD therapy (Yes, No)
- Medications for Anti-Parkinson's Disease:
 - No prior anti-PD therapy
 - Previous anti-PD therapy but no anti-PD therapy within 4 weeks prior to enrollment
 - Patients must have received stable anti-PD drug therapy for at least 4 weeks prior to enrollment and agree to maintain the original treatment regimen unchanged during the trial.
- Age at initial diagnosis (years) = (Initial diagnosis date - Birth date + 1) / 365.25, rounded to 1 decimal place. If the initial diagnosis date is missing, impute according to the following principles before calculation: if the day is missing, impute as the 1st day; if both the month and day are missing, impute as January 1st; if the year, month, and day are all missing, treat as missing.
- Age group at initial diagnosis (\leq 50 years, $>$ 50 years)
- Past and Present Medical History (excluding Parkinson's disease) (Yes, No)
- Previous surgical history (Yes, No)
- Allergy history (Yes, No)
- Modified Hoehn-Yahr Scale (Stage 0, Stage 1.0, Stage 1.5, Stage 2.0, Stage 2.5, Stage 3.0, Stage 4.0, Stage 5.0)
- Disease duration (years) = (Date of informed consent signing - Initial diagnosis date + 1) / 365.25, with results rounded to 1 decimal place. If the initial diagnosis date is missing, impute according to the following principles before calculation: if the day is missing, impute as the 1st day; if both the month and day are missing, impute as January 1st; if the year, month, and day are all missing, treat as missing.
- Type of Parkinson's Disease History (Clinically Confirmed Parkinson's Disease, Probable Parkinson's Disease, Other)

6.7. Past and Current Medical History

Code past and current medical history using the Medical Dictionary for Regulatory Activities (MedDRA; version 27.0 or above). Based on the FAS, summaries will be conducted according to the System Organ Class (SOC) and Preferred Term (PT), with detailed listings provided.

6.8. Prior and Concomitant Medications/Non-Pharmacological Therapies

Prior and Concomitant Medications

This study includes prior and concomitant medications, excluding medication for anti-Parkinson's disease, as well as anti-Parkinson's disease medications (excluding the investigational product). The World Health Organization Drug Dictionary (WHODrug, Global B3, Sep2024 or later version) will be used for coding.

Prior medication is defined as drugs with both start and end dates occurring before the first dose of study drug.

Concomitant medication is defined as any drug initiated on or after the date of the first dose of study drug, or any drug initiated before the date of the first dose of study drug and still in use on the date of the first dose of study drug.

Based on the FAS, the prior and concomitant medications of subjects, excluding medications for anti-Parkinson's disease, as well as the prior and concomitant medications for anti-Parkinson's disease (excluding investigational products), will be summarized by Anatomical Therapeutic Chemical (ATC) classification level 2 (ATC2) and Preferred Name (PN). List the subjects' prior and concomitant medications in detail.

Previous and Concomitant Non-Pharmacological Therapies

Code prior and concomitant non-drug therapies using the Medical Dictionary for Regulatory Activities (MedDRA) version 27.0 or higher.

Previous non-pharmacological therapy is defined as non-pharmacological therapy with both start and end dates occurring before the first dose of the study.

Concomitant non-drug therapy is defined as any non-drug therapy initiated on or after the date of the first dose of study drug, or initiated before the date of the first dose of study drug and still ongoing on the date of the first dose of study drug.

Based on the FAS, a detailed listing of subjects' prior and concomitant non-drug therapies will be provided.

